#### 3. INTRODUCTION AND RATIONALE

The mainstay of antenatal treatment of fetal anemia due to red cell alloimmunization is (serial) intrauterine red cell transfusions (IUT). The mainstay of postnatal treatment in hemolytic disease of the fetus and newborn (HDFN) is (1) intensive phototherapy and exchange transfusion to treat hyperbilirubinemia and prevent kernicterus, and (2) top-up transfusions to treat anemia. Up to 80% of infants with HDFN treated with IUT require at least one top-up transfusion for late anemia during the first 3 months of life, with an average of two top-up transfusions and therefore two hospital admissions per infant. Late anemia is attributed to two mechanisms: "hyporegenerative anemia" characterized by depressed erythropoiesis and "late anemia of hemolytic disease" caused by persisting antibodies, destroying newly produced erythrocytes. "Hyporegenerative anemia" occurs in particular in neonates treated with several IUTs due to bone marrow suppression. To distinct these two mechanisms, a persistence of a high antibody titer can be used. Several risk factors for late anemia have been reported, including serial IUT (due to bone marrow suppression), severity of HDFN, reduced use of exchange transfusions during the neonatal period and reduced survival of transfused red blood cells. Finally, erythropoietin deficiency is also considered as a possible contributing factor to late anemia. Erythropoietin (EPO) has been increasingly used in neonates to prevent or reduce neonatal anemia without short or long-term adverse effects. Several small studies and casuistic reports suggest that neonates with HDFN may benefit from treatment with EPO to reduce the risk of delayed anemia and subsequent top-up transfusions. However, other authors found that EPO may be less effective than expected. Due to the lack of evidence, routine use of EPO is currently not recommended. To determine a role for EPO in this group of patients, a well-designed randomized controlled clinical trial of sufficient sample size is required. Potentially, EPO stabilizes the hemoglobin levels of these infants and thus prevents anemia, hospital admissions for top-up transfusions and potential transfusion reactions, creating a more stable and natural postnatal course for patients with HDFN. In this scenario, the current

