#### 6.2 Neonatal baseline characteristics

The following variables will be recorded: birth weight, gestational age at birth, gender, Apgar score at 5 min, respiratory distress syndrome, patent ductus arteriosus, necrotizing enterocolitis, sepsis and cerebral lesions on cranial ultrasound examination, number of days of phototherapy, number of exchange transfusions, and highest bilirubin level during admission. At birth, the following measurements will be performed in umbilical cord blood as part of standard care: hemoglobin level, hematocrit, reticulocyte count, nucleated red cells (erythroblasts), iron tests (including serum iron, total iron binding capacity, transferrin and ferritin), liver enzymes (ASAT, ALAT, γGT and LDH). Additionally, EPO-levels will be measured in umbilical cord blood.

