#### 4.2 Study design

Randomized controlled trial without placebo. Included neonates will be randomized at birth to treatment with EPO (intervention group) or “standard care”, with 1:1 allocation, to be randomized in varying blocks of 4 and 6, no stratification is applied. In the treatment group, EPO (darbepoetin alfa) is administered subcutaneously at a dosage of 10  $\mu\text{g}/\text{kg}$  once a week, starting at approximately day 7, for a period of 8 weeks. Treatment is administered during weekly home visits in the treatment arm after discharge from the LUMC. Concomitant therapy with folate (0.25 mg/day) is given in both groups (standard practice). Concomitant iron therapy is given if ferritin level drops below 75 microg/l (standard practice). Weekly routine measurements of complete blood counts (including hemoglobin level, hematocrit and reticulocyte count) will be performed in both groups (standard practice). EPO is discontinued if hemoglobin level is  $\geq$  13 g/dL after at least 4 weeks of treatment with EPO. In EPO treated infants, blood pressure will be measured for safety reasons at onset of treatment, after four weeks and eight weeks. Monthly measurements of liver enzymes (aspartate aminotransferase (ASAT), alanine aminotransferase (ALAT), gamma-glutamyl transferase ( $\gamma$ GT) and lactate dehydrogenase (LDH)) will also be performed in all groups (standard practice). In addition, the neonatal EPO-level will be determined at birth in both groups. The number of postnatal transfusions received during the first 3 months of life and hemoglobin levels prior to the postnatal transfusion are recorded. After initial discharge from the LUMC, postnatal transfusions are recommended to be performed when hemoglobin levels fall below aforementioned cut-off values of hemoglobin.

Because of these clearly defined guideline and hemoglobin measures, blinding of caregivers to treatment allocation and use of a placebo was not deemed necessary.

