4.4 Sample size calculation

Based on the (scarce) results in the literature, we expect a 50% reduction in the median number of total postnatal transfusions per patient with EPO treatment, from a median of 2 to 1. For sample size calculation we hypothesized a shift in the distribution of number of transfusions per infant as depicted in Figure 1. The distribution in the 'care as usual' group are based on data from 2000-2014. Based on these expected frequencies, group sample sizes of 21 achieve 81% power to detect a difference of 1.1 between the null hypothesis that both group means are 1.9 and the alternative hypothesis that the mean of the EPO group is 0.8 with estimated group standard deviations of 1.5 and 0.9 and with a significance level (alpha) of 0.05 using a two-sided Mann-Whitney test. The drop-out percentage is estimated at 5%, adding  $(42/0.95 = 44)$  1 infant to each group's sample size.

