### 5.2 Analysis of primary and secondary outcomes

The total number of postnatal transfusions per infant from birth to the end of the follow-up period, the number of postnatal transfusions per infant  $\geq 7$  days (which is at the start of intervention in the treatment group) and the number of days of additional admissions for postnatal erythrocyte transfusions will be compared between both groups using a Mann-Whitney U test. The time from birth to first postnatal transfusion will be compared between both groups using a log rank test and will be displayed using Kaplan-Meier survival curves (in this case transfusion-free survival) by treatment group. The period of follow-up in this study is 90 days and as such the end point for included infants that do not receive transfusions during this period, is 90 days in the survival analysis. The percentage of infants requiring a postnatal transfusion up to 3 months of life will be compared between both groups using a  $\chi^2$  test. The average or median number, depending on shape of distribution, of EPO injections in the treatment arm will be reported, as well as a summary of reasons to discontinue EPO treatment.

A multiple linear regression analysis will be performed to correct the association between treatment assignment and the primary outcome (number of postnatal transfusions). The following potential

confounders identified from previous research [unpublished data] are to be corrected for if, despite randomization, there is a baseline difference between the groups: type of alloimmunization, EPO-levels at birth, number of IUTs and treatment with exchange transfusion. In case of a non-normal distribution of the number of postnatal transfusions per neonate, log transformation will be applied. If the assumptions underlying linear regression are violated, or if the value zero occurs often, a Poisson regression will be fitted. If the number of postnatal transfusions per infant <7 days of life shows a difference between the two groups, a sensitivity analysis will be performed by performing the multiple linear regression analysis (or Poisson regression) with and without the transfusions administered <7 days. This will differentiate between the clinical course of early and late anemia and will evaluate more specifically the effect of EPO treatment, which is started at 7 days of age.

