## 5.1 Figures and tables

**Figure 1. Flowchart of study participants**

**Figure 2. Kaplan Meier survival curves for time to first postnatal transfusion by treatment group**

**Figure 3. Hemoglobin course over time by treatment group**

**Table 1. Baseline demographic and clinical characteristics by treatment group**

	EPO treatment (n=22)	Standard care (n=22)
Male - n (%)		
Cesarean delivery - n (%)		
Gestational age at birth - weeks		
Number of IUTs per neonate		
Gestational age at first IUT - weeks		
Hemoglobin level at first IUT - g/dl		
Birth weight - gram		
Hemoglobin level at birth - g/dl		
Reticulocyte count at birth - ‰		
Endogenous erythropoietin at birth - U/L		
Apgar score at 5 minutes		
RhD alloimmunization - n (%)		
Rhc alloimmunization - n (%)		
Kell alloimmunization - n (%)		
Phototherapy - days		
Treatment with exchange transfusions - n (%)		
Maximum bilirubin - mg/dl		

a Value given as mean  $\pm$  SD

b Value given as median (IQR)

**Table 2. Postnatal transfusions and safety measures in EPO treated infants and infants treated according to standard care**

	EPO treatment (n=22)	Standard care (n=22)	p-value
Total number of RBC transfusions per neonate			
Number of RBC transfusions per neonate $\geq 7$ days			
Treatment with postnatal RBC transfusion - n (%)			
Number of days before first transfusion			c
Hemoglobin level at first transfusion - g/dl		-	
Initial hospitalization - days			
Additional hospitalization - days			
Infants with systolic blood pressure $\geq 2$ SD above age adjusted mean during treatment - n (%)		-	
Infants with ferritin levels $>200$ $\mu\text{g/L}$ during treatment - n (%)		-	

a Value given as mean  $\pm$  SD

b Value given as median (IQR)

c Log rank test

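### The supportive adjusted model treats exchange transfusion as a baseline confounder, although it can follow open allocation, and omits hemoglobin at birth; the primary test is unaffected

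*SAP*

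**What the plan says.** The primary endpoint is the number of postnatal transfusions from birth to 3 months (SAP 4.3), compared by an unadjusted Mann-Whitney U test with intention to treat preferred (SAP 5.1 and 5.2).

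SAP 5.2 adds a multiple linear regression, with a log transformation or Poisson model as fallback. It corrects for potential confounders if "there is a baseline difference between the groups: type of alloimmunization, EPO-levels at birth, number of IUTs and treatment with exchange transfusion". Protocol 5.10 has a shorter list (type of alloimmunization, EPO level at birth, exchange transfusion) and makes the model an optional secondary analysis.

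On timing, SAP 4.2 states "Included neonates will be randomized at birth to treatment with EPO (intervention group", with caregivers unblinded and darbepoetin starting at about day 7. SAP Section 2 describes exchange transfusion as postnatal treatment of hyperbilirubinemia. The baseline table (SAP Table 1) nevertheless has the row "Treatment with exchange transfusions - n", and Protocol 6.2 records the number of exchange transfusions among neonatal baseline characteristics.

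On hemoglobin, Protocol 6.2 says "At birth, the following measurements will be performed in umbilical cord blood as part of standard care: hemoglobin level", and Table 1 has a row for hemoglobin at birth. Neither covariate list contains it.

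**The concern.** A correction for baseline imbalance presumes that the imbalance arose by chance. That holds for variables fixed before allocation. It need not hold for a treatment decision made afterwards by staff who know the arm. The SAP rule brings exchange transfusion into the model exactly when the arms differ on it, which is when a non-random explanation is most relevant. The variable is also tied to the outcome: Protocol Section 3 lists "reduced use of exchange transfusions during the neonatal period" among the risk factors for late anemia. Conditioning on it could therefore remove or create part of an arm difference.

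Cord hemoglobin, by contrast, cannot be affected by allocation. The SAP transfusion rule (Section 4.1) is a set of hemoglobin cut-offs that starts on day 0, and the primary count includes days 0-6, before the drug is given. With 44 infants and no stratification, chance imbalance on such a variable is realistic. What is at stake is the credibility and precision of the supportive estimate.

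**Working it through.** **1. The plan's own figure.** SAP 4.4 states that "group sample sizes of 21 achieve 81% power to detect a difference of 1.1 between the null hypothesis that both group means are 1.9" and that "the mean of the EPO group is 0.8 with estimated group standard deviations of 1.5 and 0.9", at a "significance level (alpha) of 0.05 using a two-sided Mann-Whitney test".
- Root-mean-square SD = sqrt((1.5² + 0.9²)/2) = sqrt(1.53) = 1.237.
- SE of the difference at 21 per arm = 1.237 × sqrt(2/21) = 0.382.
- Power = Φ(1.1/0.382 − 1.96) = 82.2%. With the Mann-Whitney relative efficiency 3/π it is 80.4%.

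Both lie within 2 points of the stated 81%. The calculation uses no covariates, so the covariate list does not touch it.

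**2. When exchange transfusion happens relative to allocation.** Infants randomized at birth can receive it only afterwards. Protocol 5.6, however, places consent before randomization and allows it after birth within the first week; Protocol 9.2 gives parents at least 24 hours to decide. In those infants an exchange transfusion may precede allocation. The documents give no dates. The variable is therefore before allocation in some infants and after it in others.

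**3. Whether adjusting for it biases the estimate.** The documents give no exchange-transfusion rate, so this is illustration only. The simulation had 400,000 infants per scenario, a latent severity driving cord hemoglobin, exchange transfusion and a Poisson count, and linear regression on the count. The control rate was assumed to be 26%. Here d is the assumed reduction in the log count from an exchange transfusion.

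| EPO-arm rate | d | Unadjusted | Adjusted for exchange transfusion | Shift |
|---|---|---|---|---|
| 26% | 0 | −1.078 | −1.078 | 0.000 |
| 26% | 0.6 | −0.931 | −0.930 | +0.001 |
| 46% | 0 | −1.082 | −1.146 | −0.064 |
| 46% | 0.6 | −1.001 | −0.933 | +0.068 |
| 12% | 0 | −1.076 | −1.021 | +0.055 |
| 12% | 0.6 | −0.874 | −0.930 | −0.056 |

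Equal rates give no bias. Unequal rates shift the estimate by at most about 0.07 of roughly 1.0 transfusions, in either direction. With cord hemoglobin also in the model, the largest shift was 0.09 (−1.001 to −0.908).

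**4. What cord hemoglobin would add.** The documents give no correlation between cord hemoglobin and the count, so its absolute value r is assumed. Adjustment multiplies the SE by sqrt(1 − r²). At 22 per arm the SE of a standardized chance imbalance is sqrt(2/22) = 0.302, so a 1-SE imbalance shifts the unadjusted difference by r × 1.237 × 0.302.

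| r | SE multiplier | SE reduction | Shift from 1-SE imbalance |
|---|---|---|---|
| 0.2 | 0.980 | 2% | 0.07 |
| 0.3 | 0.954 | 5% | 0.11 |
| 0.4 | 0.917 | 8% | 0.15 |
| 0.5 | 0.866 | 13% | 0.19 |

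For r of 0.3-0.5 the shift is 0.112/1.1 = 10% to 0.186/1.1 = 17% of the planned difference. These figures apply to a linear model on the raw count, not to the Mann-Whitney test.

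**The case against.** The strongest reply is that nothing decisive is affected. The planned test is unadjusted, and the model is conditional and, in the Protocol, secondary. This stands: a reader might infer that the primary result is biased or underpowered, and the documents do not support that.

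Second, a reader might infer that adjustment removes part of the drug's effect. Darbepoetin starts near day 7, so it cannot change an exchange transfusion given earlier. Bias then requires knowledge of the arm to alter the management of hyperbilirubinemia, and no passage suggests that it does. If use did differ, the unadjusted estimate would carry that co-intervention, and adjustment could come nearer to the drug's own effect. The simulated cases with d = 0.6 show this: the adjusted values return to about −0.93, the value under equal rates. With d = 0 the opposite happens. This stands too, and it is why exchange transfusion belongs in a sensitivity analysis and should not be discarded.

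Third, the SAP's list comes from unpublished data, and nothing in the documents shows that cord hemoglobin predicts better than the factor it would replace. That is fair. The case for it rests on timing and on its place in the transfusion rules, not on demonstrated predictive strength. Protocol 5.2 also requires symptoms between 7.2 and 8.8 g/dL, so hemoglobin is part of every stated trigger but not always the whole of it.

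Fourth, the shift in step 4 is r times the SE of the difference (1.237 × sqrt(2/22) = 0.373). It is ordinary chance variation that the test's error rate already covers, not bias. That is correct; the gain is precision and a clearer supportive estimate.

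**Conclusion.** The point holds for the supportive adjusted model only. Its covariate set mixes variables fixed before allocation with one that may follow open allocation, and it leaves out a birth value measured as standard care.

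The possible bias from exchange transfusion depends on use differing by arm because of open allocation. It is probably small, and the documents cannot size it; the 0.07 rests on assumed rates and effects. The benefit from cord hemoglobin is modest to moderate: an SE reduction of about 2-13% for assumed r of 0.2-0.5.

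Two stronger statements should not be made. One is that exchange transfusion always follows randomization; consent in the first week means that it may not. The other is that the adjusted estimate is known to be biased; that would need an arm difference caused by knowledge of allocation, for which the documents give no evidence.

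**What to change.** - **SAP 5.2:** restrict the adjusted model to covariates fixed before allocation. Replace 'treatment with exchange transfusion' by 'hemoglobin level at birth (cord blood)', alongside type of alloimmunization, EPO level at birth and number of IUTs. Include cord hemoglobin whether or not the arms differ on it; left under the baseline-difference condition, the precision gain is not secured.
- **Protocol 5.10:** align its list with the SAP's. It currently also lacks number of IUTs.
- **Exchange transfusion:** report it by arm, with its timing relative to randomization, and adjust for it only in a labelled sensitivity analysis.
- **SAP Table 1:** put phototherapy days, exchange transfusion and maximum bilirubin under a heading such as 'course after birth'.
- **Timing of randomization:** reconcile randomization at birth (SAP 4.2) with consent during the first week (Protocol 5.6).

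The cost is wording, settled before database lock and unblinding. The swap leaves the number of listed factors unchanged, which matters with 44 infants. Cord hemoglobin is already measured; what is needed besides is the timing of exchange transfusions. The one downside is a simple baseline imputation for any infant without a cord value. The primary test and the sample size stay as they are.

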A linear mixed model will be fitted to assess the course of hemoglobin in the treatment and control group which will be graphically depicted. Each infant has repeated weekly hemoglobin measurements as advised in the protocol, but as the frequency of measurements is not mandatory, the data may show missing values at different time points. These missing values are expected to be at random and not completely at random, as it can be anticipated that a measurement is omitted after a previous positive (high) hemoglobin measure which justifies a longer interval between measurements due to the low risk of sudden anemia warranting transfusion. The course of hemoglobin in both groups is expected to have a negative slope after birth due to ongoing hemolysis and a physiological decline of fetal hemoglobin, which will stabilize over the course of several weeks and then show a positive slope as normal physiology recovers or is artificially raised with postnatal transfusions.

To account for the correlation between repeated measurements on the same subject, a random intercept will be included and, if model fit improves, a random slope in the model. The fixed effects will be treatment, time (with a non-linear functional form that will later be determined to match the shape of the expected de- and increase described above) and the interaction treatment\*time. The primary assessment of whether the two groups differ in their hemoglobin course over time will be based on a test on the interaction treatment\*time (a test which will correspond with the most suitable functional form).

[figure not shown]
Throughout the planned analyses, a p-value below 0.05 is regarded as statistically significant. Statistical analysis will be performed using IBM SPSS Statistics 23.0 (Chicago, Illinois, USA).

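### The hemoglobin-course test pairs a non-linear time interaction with at most one random slope per infant, so its type I error is not controlled at 5% if infants differ in curve shape

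*SAP*

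**What the plan says.** All of the model is in SAP 5.2.

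- **Fixed effects:** treatment, "time (with a non-linear functional form that will later be determined to match the shape of the expected de- and increase described above"), and their interaction.
- **Test:** "The primary assessment of whether the two groups differ in their hemoglobin course over time will be based on a test on the interaction" of treatment with time. The level is general: "Throughout the planned analyses, a p-value below 0.05 is regarded as statistically significant".
- **Within-infant correlation:** "a random intercept will be included and, if model fit improves, a random slope in the model".
- **Expected shape:** a decline, a stable phase, and the curve will "then show a positive slope as normal physiology recovers or is artificially raised with postnatal transfusions".
- **Data:** "Each infant has repeated weekly hemoglobin measurements as advised in the protocol, but as the frequency of measurements is not mandatory", so gaps are expected and are argued to be missing at random. "The period of follow-up in this study is 90 days".

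The SAP is silent on random effects for any other time term, on the residual covariance, on robust standard errors and on the denominator degrees of freedom. It gives no variance for hemoglobin of any kind.

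Hemoglobin course is the last secondary endpoint in SAP 4.3 and is to be shown in Figure 3. It has no row in SAP Table 2 and is not among the endpoints in protocol 5.5.

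**The concern.** The interaction asks whether the two mean curves differ in shape. The right yardstick is how much infants within an arm differ in shape. A random intercept lets infants differ in level, and one random slope lets them differ along one direction in time. If the time function has two or more terms, variation between infants in the remaining terms has nowhere to go but the residual. The model then treats that variation as fresh noise at each reading and averages it over up to 44 × 13 = 572 readings, when it should be averaged over 44 infants. Standard errors of the curved interaction terms come out too small. Selecting the slope by model fit does not help, because the other terms are not among the named candidates.

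The SAP's own description makes such variation likely. Rates of loss and recovery differ between infants. SAP 4.4 expects a control mean of 1.9 transfusions with SD 1.5, so the number and timing of upward jumps will differ too. The missing-at-random argument also leans on the covariance model being adequate.

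At stake is a false statement that darbepoetin changes the course of hemoglobin. In an open-label trial this could be read as mechanistic support for the primary result.

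**Working it through.** **1. The plan's own figure.** For this test there is only the nominal 0.05. The power statement in SAP 4.4 concerns the primary endpoint. It reproduces closely: pooled SD √((1.5² + 0.9²)/2) = 1.237, and a t-test with 21 per group has 80.3% power against the stated 81%. It is used here only for group size: 42/0.95 = 44.2, taken as 44, or 22 per arm.

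**2. Inputs.** From the SAP: 22 per arm, weekly readings over 90 days (13 values), intercept plus at most one slope, level 0.05. Assumed, because the documents give none: intercept SD 1.2, slope SD 0.6 per six weeks, residual SD 0.8 g/dL, and a range for the SD *q* (g/dL) of infant-specific curvature.

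**3. Closed form, quadratic time.** Code time as t = −1, −5/6, …, 1, in units of six weeks from mid follow-up. Then S = Σ(t² − mean t²)² = 3.511 − 13 × 0.3889² = 1.545.

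- True variance of one infant's fitted curvature: q² + 0.64/S.
- Variance the model credits: (0.64 + q²S/11)/S, because the omitted curvature is spread over 13 − 2 = 11 residual degrees of freedom per infant.
- For q = 0.5: 0.25 + 0.414 = 0.664 against 0.675/1.545 = 0.437. The ratio is 1.52, so the standard error should be √1.52 = 1.23 times larger. The joint two-term test rejects when χ²₁ + 1.52·χ²₁ exceeds 5.99, which happens 9.4% of the time.
- For q = 1.0: 1.414 against 0.780/1.545 = 0.505. The ratio is 2.80 and the rejection rate is 20.1%.

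**4. Null simulation of the planned model.** REML, slope kept if AIC improves, 600 trials per row. Rejection rates are in percent, with 42 then 500 denominator degrees of freedom.

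| Curvature SD | Closed form, quadratic | Simulated, quadratic | Simulated, cubic |
|---|---|---|---|
| 0 | 5.0 | 4.2 / 5.5 | 3.8 / 4.3 |
| 0.25 | 6.1 | 5.0 / 6.3 | 4.8 / 5.5 |
| 0.5 | 9.4 | 10.0 / 10.7 | 8.0 / 8.8 |
| 0.75 | 14.5 | 14.2 / 15.0 | 10.5 / 12.2 |
| 1.0 | 20.1 | 17.8 / 19.5 | 15.0 / 17.2 |
| 1.5 | 29.7 | 27.0 / 29.8 | 23.0 / 25.0 |

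The two routes agree. With serially correlated deviations in place of curvature (quadratic), the rate was 10.5-13.3% at correlation 0.3 and 22.2-24.3% at 0.8.

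**5. Simulations with transfusion jumps.** Sets B, C and D used the SAP 4.1 cut-offs. The assumed rise was +3 g/dL per transfusion, or +2 where stated.

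| Set | Transfusions per infant | Quadratic | Cubic |
|---|---|---|---|
| A (+2.5 or +3) | 1.0-1.1 | 18-21% | – |
| B (+2 or +3) | 1.3-1.7 | 7-13% | 11-18% |
| C (+2 in some variants) | about 0.5 | 10-15% | 14-20% |
| C | about 2.0 (SD 1.3) | 4-6% | 11-13% |
| C | about 2.4 | 6-7% | 14-17% |
| C, identical underlying loss and recovery | not tabulated | 2-3% | 7-8% |
| D | 1.93 (SD 1.59) | 16% | 24% (spline 22%) |

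Most results lie between 8% and 20%. The exceptions are low values for the quadratic in set C and high ones for the flexible bases in set D. Sets C and D both give about two transfusions per infant yet differ widely. Matching the planned transfusion count therefore does not fix the rate.

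**6. Tests that use the infant as the unit.** Hotelling's T² on each infant's fitted curve coefficients rejected in about 3-7% of null trials. Giving every time term a random effect makes the Wald F, on balanced data, a rescaled T². Referred to 42 degrees of freedom, it rejects 5.4% of the time with two time terms and 5.9% with three.

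**7. A reading under which the planned test holds.** If one single-degree-of-freedom non-linear function of time carries both the random slope and the interaction, the rate was 4-7% (300 trials per setting).

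**The case against.** The best reply is that the SAP is under-specified, not wrong. It does not say the random slope is on linear time, and it does not say the residuals are independent. A single time function carrying both slope and interaction would fit the wording and would hold close to 5%. That stands as a possibility. However, a fall, a plateau and a rise normally calls for more than one term, and the only device the SAP names for within-infant correlation is the intercept and one slope.

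The second reply concerns size. A reader might infer from sets such as D that the error rate is at least 12%, or some other definite figure above 5%. The documents do not support that. They contain no hemoglobin variances, and the rate falls to about 5% when infants differ little in curvature. Rates of 35-40% for a random intercept alone should not be attributed to the plan either, since AIC kept the slope in 99-100% of simulated trials.

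Third, importance. A reader might call this the only planned evidence on hemoglobin, or say that Figure 3 will show bands that are too narrow. Hemoglobin at first transfusion is also a secondary endpoint in SAP 4.3, although it is tied to the transfusion cut-offs. The transfusion endpoints depend on hemoglobin as well. No band is planned for Figure 3.

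Finally, SAP 4.2 keeps the statistician blinded until the plan is final and the database is locked. That limits a data-driven choice of time function, but it does not correct the standard errors.

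**Conclusion.** The point holds as a loss of error control, not as a fixed rate. With a multi-term time basis and infants who differ in curve shape, the interaction test described in SAP 5.2 rejects too often under the null. Under assumed variances the rate runs from about 5% to about 30%, typically 8-20% when loss, recovery and transfusion jumps vary between infants. An infant-level test gives about 3-7%.

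The mechanism follows from the SAP's text. The size depends on assumed curvature, serial correlation, rise per transfusion and time basis. The test should be corrected before unblinding, but it concerns one secondary endpoint. The primary Mann-Whitney comparison does not use this model.

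**What to change.** In SAP 5.2, before unblinding:

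1. Name one time basis, for example a spline with stated knots.
2. Choose one route to a valid interaction p-value:
   - random effects for every time term in the interaction, or a stated serial residual covariance, with a named small-sample degrees-of-freedom method; or
   - the planned mean model, with the p-value from permuting allocation across infants.
3. If Figure 3 carries uncertainty bands, base them on the same infant-level error.

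The first route addresses the covariance that the missing-at-random argument relies on. The permutation route protects the error rate but leaves that covariance as it is.

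The cost is a paragraph of SAP text and, for permutation, a short script. The richer random effects may fail to converge with 44 infants, so a fallback should be named. The test will show less apparent power, because the planned version overstates it.

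### The SAP's hemoglobin model estimates an arm difference at birth that randomization makes zero in expectation; the interaction test stays valid but is less efficient than it could be, by an amount the documents do not fix

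*SAP*

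**What the plan says.** SAP 5.2 lists the fixed effects of the hemoglobin model: "The fixed effects will be treatment, time (with a non-linear functional form" to be settled later), and the treatment-by-time interaction. The assessment of whether the courses differ "will be based on a test on the interaction". For the random part, "a random intercept will be included and, if model fit improves, a random slope in the model".

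The time origin is not stated, but the expected course in each arm "is expected to have a negative slope after birth due to ongoing hemolysis", which points to birth.

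On timing, SAP 4.2 says: "Included neonates will be randomized at birth to treatment with EPO (intervention group") or standard care, with darbepoetin starting at about day 7. Protocol 6.2 says: "At birth, the following measurements will be performed in umbilical cord blood as part of standard care: hemoglobin level" and other tests. SAP Table 1 lists hemoglobin at birth as a baseline characteristic.

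Neither document gives the arms a common mean at birth in this model or adjusts the model for hemoglobin at birth. The conditional covariates in SAP 5.2 belong to the regression for the primary outcome, and hemoglobin at birth is not among them.

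**The concern.** Cord hemoglobin is fixed before allocation. Protocol 5.6 allows consent during the first week, but the cord value still comes first. Any arm difference at birth is therefore due to chance. A free main effect spends information on a quantity whose expectation is known to be zero. The interaction, the only thing tested, then measures departure from each arm's own fitted starting level instead of from a shared one.

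At stake is precision for one secondary end point, the one that describes the biological response most directly. With 22 infants per arm and no stratification, the standard error of the arm difference in mean cord hemoglobin is sqrt(2/22) = 0.30 SD. A visible imbalance at birth is therefore quite possible in the one trial that is run.

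**Working it through.** **The plan's own figure.** No power or precision is stated for the hemoglobin model. The only stated figure is for the primary end point: 81% power with 21 per arm. From the stated SDs, sqrt((1.5² + 0.9²)/2) = 1.237, and 1.1/1.237 = 0.889. Then 0.889 × sqrt(21/2) − 1.96 = 0.92, a power of about 82% by normal approximation, close to the stated 81%. The drop-out allowance is 42/0.95 = 44.2. Neither depends on the hemoglobin model.

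**Inputs.** From the SAP: fixed effects, tested term and random effects (5.2), weekly measurements (5.2: "Each infant has repeated weekly hemoglobin measurements as advised in the protocol"), 90 days of follow-up, 1:1 allocation. Assumed, because the documents do not give them: 14 time points (weeks 0 to 13, no gaps), within-infant correlation (ICC) ρ of 0.3 to 0.7, slope variance of 0 to 1 times the intercept variance over full follow-up, and the shape of the treatment effect.

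**Simplest case by hand.** Take a random intercept only, total variance 1, and an arm difference growing linearly from birth.
- Σt = 91, so (Σt)² = 8281; Σt² = 819.
- Free difference at birth: the information on the slope difference is proportional to 819 − 8281/14 = 227.5.
- Common mean at birth: it is proportional, with the same factor, to 819 − 8281k, where k = ρ/(1 + 13ρ).
- ρ = 0.3: k = 0.3/4.9 = 0.0612, giving 312.0; ratio 312.0/227.5 = 1.37.
- ρ = 0.5: k = 0.5/7.5 = 0.0667, giving 266.9; ratio 1.17.
- ρ = 0.7: k = 0.7/10.1 = 0.0693, giving 245.1; ratio 1.08.

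A simulation of 20,000 runs at ρ = 0.5 gave a variance ratio of 1.17. Type I error was 0.050 both with the free difference and with the common mean.

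**Other cases.** The same comparison by generalized least squares gives these ratios of the noncentrality of the interaction test, from ρ = 0.3 to ρ = 0.7:

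| Effect shape | Random intercept only | Slope variance equal to intercept variance |
|---|---|---|
| Linear from birth | 1.37 to 1.08 | 1.21 to 1.02 |
| Linear from day 7 | 1.29 to 1.06 | about 1.14 to 1.00 |
| Rising to a plateau | about 1.6 to 1.12 | about 1.4 to 1.06 |

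Linear, quadratic, cubic and categorical time give nearly the same values in the first two rows. For an effect that starts at day 7 and reaches its plateau at week 5, a straight-line time term with random intercept only gives about 1.75 at ρ = 0.3. If correlation decays with time, the ratios are larger still, about 1.6 or more. No case fell below 1.

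**Meaning of a ratio.** Noncentrality is proportional to the number of infants. On N = 44, a ratio of 1.10 is worth 44 × 0.10 = 4.4 infants, 1.37 is worth 16.3, and 1.60 is worth 26.4, for this end point only. If the planned test had 80% power, the constrained test would have about 83-84% at 1.10 and 91-93% at 1.37.

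**The case against.** Treatment, time and their interaction is a standard and valid specification, and preferring a constrained model is partly a matter of taste. The SAP leaves the functional form open, does not fix the time origin, and does not say that cord hemoglobin is the first repeated value. The end point is the last listed of several secondary ones and has no power calculation. All of this stands, and it limits the weight of the point.

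Four stronger readings are tempting, and the documents do not support them:
- *A definite cost, such as 10% to 37% more infants.* That range is what ρ = 0.65 to 0.3 gives in one scenario (random intercept only, effect linear from birth). With the random slope that the SAP allows and an effect starting at day 7, the loss can be close to zero; with a plateau it can exceed 37%.
- *The baseline is discarded.* If cord hemoglobin is in the data set, it stays in the model as a repeated measure. With a smooth time function, the difference at time zero is also estimated from the later values, so the test is not a plain comparison of change from birth. What goes unused is the equality of the arms at birth.
- *The test is biased by chance imbalance.* Type I error is 0.050 either way. Imbalance can colour the reading of a single trial, but the test is valid.
- *The trial is too small because of this.* The primary Mann-Whitney comparison and N = 44 do not use this model.

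One objection also bears on the remedy. SAP 5.1 removes infants withdrawn before day 7 from all analyses, in an open-label trial. Equality at birth holds in expectation for all randomized infants, but only approximately in the analysis set.

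**Conclusion.** The point holds as a minor matter of efficiency. Under the natural reading of SAP 5.2, the model estimates an arm difference at birth that randomization makes zero in expectation, and the interaction test is valid but less efficient than it could be. Over the assumed ICC of 0.3 to 0.7, with or without a random slope, equality at birth raises the noncentrality by about 0% to 60-75%, depending on slope variance, time basis and effect shape, and by more if correlation decays with time. The direction is firm: no scenario showed a loss from the constraint. The size is not, because the documents give no hemoglobin covariance and no effect curve. The conclusion also rests on time being counted from birth and on cord hemoglobin entering as the first repeated value.

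**What to change.** In SAP 5.2, where the time function still has to be settled, add that:
- time zero is birth and cord hemoglobin is the first repeated value;
- the arms share one mean at birth: the time functions equal zero at birth and there is no treatment main effect;
- if time is categorical, the arm contrast at birth is set explicitly to zero, because deleting the main effect alone only reparametrizes the model;
- all treatment-by-time terms are tested jointly.

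Report the unconstrained model as a sensitivity analysis, because of the exclusion of withdrawals before day 7.

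The cost is a short SAP edit before database lock. The model has one parameter fewer. Cord hemoglobin is already collected as standard care, so no data are added, and the primary analysis and sample size do not change.
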